#### 6.4 Graft versus Host Disease

Use of flotetuzumab has not been evaluated in the post-allo-HCT setting, therefore the impact of flotetuzumab on acute or chronic GVHD is unknown. Theoretically, the mechanism of action of flotetuzumab may redirect allo-reactive T cells toward malignant cells and thus reduce GHVD. In pre-clinical pharmacodynamic data, flotetuzumab displays a 10-fold greater affinity for human CD123 to favor initial binding to the CD123+ target

cell and minimize CD3 engagement in the absence of target cells. It is also possible that there will be no impact of flotetuzumab on the incidence or severity of GVHD, or that it will exacerbate GVHD. The administration of a DLI is associated with GVHD rates as high as 60-70%, depending on cell dose and other factors. Therefore, it is expected that patients who receive a DLI concurrent with flotetuzumab may experience new onset GVHD or worsening of pre-existing GVHD.

Accordingly, patients with active GVHD requiring systemic immunosuppression with more than 0.5mg/day prednisone will be excluded from the trial; in addition, careful monitoring for interval development of new or worsening GVHD for patients on trial is warranted.

Acute and Chronic GVHD assessments (See Appendices F and G) will be performed to evaluate the presence of acute and chronic GVHD at screening/baseline, prior to initiation of Cycle 1 and prior to the initiation of Cycle 2, with documentation as below (Section 7.7.1 and 7.7.2). Additionally, patients should be monitored during treatment for development of new or worsening GVHD with appropriate assessment/grading as clinically indicated in the opinion of Investigators.

**6.4.1 Acute GVHD Assessment**

Acute GVHD assessment will be documented with date of onset, grade, and organs affected (see Appendix F). Of note, evaluation for alternative etiologies for new or worsening rash, LFT changes or diarrhea should be pursued according to institutional practice and standards of care. Rashes, LFT elevations and diarrhea determined to be explained by an alternative etiology (i.e. not due to aGVHD) should not be included in the Acute GVHD Assessment.

**6.4.2 Chronic GVHD Grading/Assessment**

Chronic GVHD Assessment will be documented with date of onset, grade, and organs affected. See Appendix G. Of note, evaluation for alternative etiologies for new or worsening findings on the below listed assessments should be pursued according to institutional practice and standards of care. For example, rashes, LFT elevations and diarrhea determined to be explained by an alternative etiology (i.e. not due to cGVHD) should not be included in the Chronic GVHD Assessment.

**6.4.3 Dose Delays and Modifications for aGVHD and cGVHD**

***Table 7: Dose Delays and Modifications for aGVHD***

MAGIC Grade I GVHD	The presence of new or worsening MAGIC Grade I GVHD should warrant standard of care therapies for commensurate GVHD level and does not require any dose modifications to the flotetuzumab.
---------------------------	--

MAGIC Grade II GVHD	The presence of new or worsening MAGIC Grade II GVHD should warrant standard of care therapies for commensurate GVHD and the does not require any dose modifications to the flotetuzumab. Persistent Grade II GVHD not improving with SOC interventions and supportive care within 24-48 hours requires a 25-50% dose reduction in flotetuzumab with continued SOC interventions, supportive care and continued monitoring of aGVHD severity. Uptitration of flotetuzumab to target dose may be attempted as per CRS protocol upon improvement of GVHD Grade to Grade I or better. However, persistent Grade II GVHD not improving with SOC interventions and with 25-50% dose reduction after 48-72 hours requires an immediate hold of flotetuzumab. Reinitiation of flotetuzumab with resolution of GVHD severity to Grade I or better can be attempted, resuming at 25-50% of the target dose and uptitration as per CRS protocol.
MAGIC Grade III GVHD	The presence of MAGIC Grade III GVHD should warrant standard of care therapies for commensurate GVHD and requires immediate hold of flotetuzumab. SOC interventions and supportive cares should be continued with daily assessment of GVHD Grade. Reinitiation of flotetuzumab with resolution of GVHD severity to Grade I or better can be attempted, resuming at 25-50% of the target dose and uptitration as per CRS protocol.
MAGIC Grade IV GVHD	The presence of MAGIC Grade IV GVHD should warrant standard of care therapies for commensurate GVHD and requires immediate hold of flotetuzumab. SOC interventions and supportive cares should be continued with daily assessment of aGVHD Grade. Reinitiation of flotetuzumab should not be attempted.

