### Schedule of Administration:

Two schedules of administration were evaluated in the Phase 1 dose escalation and first cohort (n=30) of the Phase 2 cohort expansion, including: 1) a 4-day on/3-day off each week administration schedule for 28 days and 2) a continuous infusion for the entire 28-day cycle. Ultimately, both approaches were shown to be feasible, however the continuous infusion schedule was selected to carry forward for the remainder of the dose expansion cohorts (n=132), because continuous infusion without 3-day breaks offered improved safety with respect to adverse events (CRS) and improved anti-leukemic activity (some patients were observed to have transient increases in peripheral blast counts during the off days).

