## **1.2 Risk/Benefit Assessment**

### **1.2.1 Known Potential Risks**

As of the data cut-off date of 22 January 2021 from the most current MacroGenics IB v11.0, flotetuzumab has been evaluated in the ongoing first-in-human monotherapy clinical study (CP-MGD006-01). Overall, the preliminary safety profile of flotetuzumab does not show any unexpected, significant, or rare safety

findings and confirms the safety observations are consistent with the mechanism of action of flotetuzumab or with the patients' underlying disease.

Infusion-related reaction (IRR, including cytokine release syndrome (CRS)), is the only important identified risk based on the observations from the 81 patients in this study and from the mechanism of action of flotetuzumab. Cumulatively, 71/81 patients (87.6%) experienced at least one IRR or CRS event. The majority of patients experiencing infusion-related reactions (including CRS) had reactions that were mild to moderate in severity (62/71), whereas 9 patients experienced at least 1 severe (Grade 3) event. None of these events have been life-threatening or fatal. Infusion-related reactions (including CRS) typically occurred during the initial 48 hours of the first infusion of flotetuzumab. Infusion-related reaction symptoms typically included pyrexia, chills, hypotension, tachycardia, and/or respiratory symptoms (e.g., tachypnea, hypoxia). Most of these events were considered possibly, probably, or definitely related to flotetuzumab. Infusion-related reaction (including CRS) events have been manageable with treatment interruption, dose reduction, early use of tocilizumab, and medical intervention, with antipyretics, antihistamines, and corticosteroids. Notably, the stepwise lead-in dosing is associated with a reduced frequency and/or severity of IRR/CRS.

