### **1.3 Overall Study Design and Plan**

This is an open-label, single-arm, single-center Phase 2 study to evaluate for efficacy, safety and tolerability of flotetuzumab administered as a single agent and/or in combination with DLI in patients with relapsed AML post-allo-HCT.

The study is designed to include 2 cycles of treatment. During Cycle 1, patients will be administered flotetuzumab as a continuous IV infusion with a week 1 ramp up to goal/target dose of 500ng/kg/day, which will be continued for the remaining 21 days of a 28-day (4-week) cycle (Cycle 1). Patients found to meet the primary endpoint of complete remission with incomplete hematologic recovery (CRi) or better on their C1D28 response assessment (bone marrow biopsy) will continue on to Cycle 2 of flotetuzumab administered as a continuous IV infusion at a target dose of 500ng/kg/day for an additional 28-day cycle (Cycle 2). Patients found to be deriving clinical benefit as evidenced by stable disease (SD) or a partial remission (PR) on their C1D28 response assessment (bone marrow biopsy) may also continue to Cycle 2 of flotetuzumab at the same dose at the discretion of the treating physician and investigator. Patients may receive a DLI concurrently with flotetuzumab treatment in Cycle 1 and/or Cycle 2 at the discretion of the investigator and treating physician. DLI, if administered, will be given on or after Day 8 of the respective cycle. Of note, if patients are off flotetuzumab for >72 hours between end of C1 and beginning of C2, they will require repeat week 1 ramp up to goal/target dose of 500ng/kg/day. Patients found to have progressive disease (PD) on their C1D28 response assessment (bone marrow biopsy) will proceed off study with SOC. All patients who receive investigational agent will then be followed for treatment response and safety monitoring.

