### 5.2.2 Cycle 2 Flotetuzumab Consolidation

Patients meeting the primary endpoint of CR/CRi and patients with PR/SD (with permission of the investigator) will receive Cycle 2 flotetuzumab pre-medications and a continuous infusion of flotetuzumab (Tables 1 & 3), beginning within 2 weeks of completing Cycle 1.

- Patients will be admitted to the hospital and pre-medications administered on Day 1.
  - If patients have been off flotetuzumab for >72 hours, then the dose escalation ramp will begin on Day 1 and will consist of continuous ramp infusion of flotetuzumab starting at 30 ng/kg/day with increasing dose over 7 days to a target dose of 500 ng/kg/day. Patients will then continue on flotetuzumab for additional 21 days at target dose of 500 ng/kg/day (28 days total).
  - If patients have been off flotetuzumab ≤72 hours, then patients will receive flotetuzumab dosed at 500 ng/kg/day continuous infusion for a total of 4 weeks (28 days).
- At the end of Cycle 2 (Day 28), patients will undergo bone marrow biopsy for disease response assessment and correlative studies, and proceed to the follow-up phase of the study.

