	
 
• Corticosteroids may be used for Grade 2 IRR/CRS that does not respond to other measures, including tocilizumab
 
• Continue infusion at reduced rate and slowly increase infusion rate to the original rate gradually by half-rate increments (i.e., if rate is reduced from 5 mL/hr to 2.5 mL/hr increase to ~3.75 mL/hr, then 4.5 mL/hr, then 5 mL/hr) after stabilization or resolution of symptoms every 4-6 hours, as tolerated. A more gradual increase in the rate of infusion may be undertaken after consultation with the PI.
 
• Report as an immediately reportable event (IRE);
 
• Report the event as a serious adverse event (SAE), if appropriate.
 
• Monitor for worsening condition.
 

Grade 3 Infusion Reaction and infusion-related events
	
 
• Stop the infusion,
 
• TO AVOID EXACERBATION OF INFUSION REACTION OR CRS: DO NOT FLUSH THE TUBING – ASPIRATE RESIDUAL DRUG FROM THE PORT LUMEN;
 
• Administer IV fluids, diphenhydramine 50 mg IV, acetaminophen 1000 mg PO or ibuprofen 400 mg PO for fever, and oxygen and bronchodilators for mild bronchospasm, as appropriate.
 
• Provide appropriate circulatory support including vasopressors as medically indicated;
 
• If not already performed, obtain infectious work-up as clinically indicated (UA, blood cultures, imaging, etc) and consider empiric antibiotics per institutional guidelines
 
• Administer tocilizumab if not administered previously. If administered previously, an additional dose may be administered in 8 hours for prolonged or recurrent episodes, with a maximum total of up to 4 doses for each CRS event.
 
• Grade 3 IRR/CRS that is refractory to tocilizumab should be treated with corticosteroids; doses of dexamethasone (or equivalent) of greater than 30 mg may be required.
 
• Resume the infusion at previously tolerated dose once the infusion reaction has resolved or decreased to Grade 1. Increase dose rate to the original rate, per protocol, e.g., 500 ng/kg/day, by increasing the dose in near double increments as tolerated after stabilization or resolution of symptoms every 4-6 hours. A more gradual increase in the rate of infusion may be undertaken after consultation with the PI.
 
• Report the event as a serious adverse event (SAE), if appropriate.
 

Grade/Event	Procedures for Management

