	
 
• Discontinue the infusion if not resolved to Grade 1 within 72 hours.
 

Grade 4 Infusion reactions and infusion-related events	
 
• Stop the infusion and disconnect the infusion tubing from the patient;
 
• TO AVOID EXACERBATION OF INFUSION REACTION OR CRS: DO NOT FLUSH THE TUBING – ASPIRATE RESIDUAL DRUG FROM THE PORT LUMEN;
 
• Administer IV fluids, diphenhydramine 50 mg IV, acetaminophen 1000 mg PO or ibuprofen 400 mg PO or paracetamol 1000 mg PO for fever, and oxygen and bronchodilators for mild bronchospasm, as appropriate;
 
• Provide appropriate ventilator and circulatory support as medically indicated;
 
• If not already performed, obtain infectious work-up as clinically indicated (UA, blood cultures, imaging, etc) and consider empiric antibiotics per institutional guidelines
 
• Agents including those listed below have been described in the management of patients with severe complications of cytokine storm and/or severe immune-related adverse events, and may be required:               
 
○ high doses of corticosteroids above dexamethasone 30 mg (or equivalent)
 
○ tocilizumab (anti-IL6 receptor) 8 mg/kg IV, administered every 8 hours as indicated with a maximum total of up to 4 doses for each CRS event
 
 
 
• Notify the PI immediately;
 
• Report the event as an SAE. Patients who have a Grade 4 IRR/CRS should not receive further flotetuzumab.
 

Grade 5 Infusion reactions and infusion-related events	
 
• Notify the PI or designee immediately.
 
• Report the event as an SAE.
 

\* Table provides guidelines but treating physician should follow their discretion to manage and grade CRS/IRR

Other types of adverse reactions may be observed during infusion that are not interpreted as related to cytokine release, but may be related to flotetuzumab. Such reactions should be diagnosed, graded and managed according to best practices.

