***Table 8: Dose Delays and Modifications for cGVHD (see NIH cGVHD Severity Score in Appendix G)***

Mild cGVHD	The presence of new or worsening Mild cGVHD should warrant standard of care therapies for commensurate GVHD level and does not require any dose modifications to the flotetuzumab.
Moderate cGVHD	The presence of new or worsening Moderate cGVHD when baseline assessment prior to flotetuzumab was rated as Mild or better should warrant standard of care therapies

	for commensurate GVHD and the does not require any dose modifications to the flotetuzumab. Persistent Moderate cGVHD not improving with SOC interventions and supportive cares within 24-48 hours requires a 25-50% dose reduction in flotetuzumab with continued SOC interventions, supportive cares and continued monitoring of cGVHD severity. Uptitration of flotetuzumab to target dose may be attempted as per CRS protocol upon improvement of cGVHD to Mild or better. However, persistent Moderate cGVHD not improving with SOC interventions and with 25-50% dose reduction after 48-72 hours requires an immediate hold of flotetuzumab. Reinitiation of flotetuzumab with resolution of cGVHD severity to Mild or better can be attempted, resuming at 25-50% of the target dose and uptitration as per CRS protocol.
Severe cGVHD	The presence of Severe cGVHD should warrant standard of care therapies for commensurate GVHD and requires immediate hold of flotetuzumab. SOC interventions and supportive cares should be continued with daily assessment of cGVHD Grade. Reinitiation of flotetuzumab should not be attempted.

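### Tables 7 and 8 restart flotetuzumab at 125-250 ng/kg/day after a GVHD hold with no limit on time off drug, while more than 72 hours off between cycles requires a ramp from 30 ng/kg/day

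*Combined protocol and SAP*

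**What the plan says.** Section 6.4.3 governs flotetuzumab when GVHD appears on treatment. Under Table 7, Grade III acute GVHD means an immediate hold. Grade II leads to a hold only if it persists through 24-48 hours of standard care and then 48-72 hours at a reduced dose. In both cases, once GVHD is Grade I or better, reinitiation "can be attempted, resuming at 25-50% of the target dose and uptitration as per CRS protocol". Table 8 treats moderate chronic GVHD the same way: "Reinitiation of flotetuzumab with resolution of cGVHD severity to Mild or better can be attempted", at the same fraction of target. Grade IV acute and severe chronic GVHD allow no restart. The only trigger for restart is GVHD severity; neither table mentions time off drug.

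Between cycles, time off drug decides. Section 1.3 says that "if patients are off flotetuzumab for >72 hours between end of C1 and beginning of C2, they will require repeat week 1 ramp up". Section 5.2.2 repeats it: "If patients have been off flotetuzumab for >72 hours, then the dose escalation ramp will begin on Day 1", from 30 to 500 ng/kg/day over 7 days. After 72 hours or less, the patient goes straight to 500.

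For dose increases after CRS, the Grade 3 row of Table 6 returns to the original rate "by increasing the dose in near double increments as tolerated after stabilization or resolution of symptoms every 4-6 hours". For an interruption of more than 24 hours, Section 6.2 asks that the Table 4 premedication schedule be followed. No section requires a re-ramp after an interruption within a cycle.

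**The concern.** The between-cycle rule applies to patients who have just had Cycle 1, planned as 22 days at 500 ng/kg/day. The protocol therefore already judges that prior exposure does not remove the need for a ramp after more than 72 hours off. A patient held mid-cycle may have had less exposure, yet can restart at 125-250.

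CRS is what is at stake. Section 1.2.1 names infusion-related reactions including CRS as the only important identified risk, and says that "the stepwise lead-in dosing is associated with a reduced frequency and/or severity of IRR/CRS". Section 1.1.7 preferred continuous infusion partly because avoiding three-day breaks gave better CRS safety, and it records that the lead-in start was lowered from 100 to 30 ng/kg/day.

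GVHD holds are foreseeable. DLI is allowed from Day 8 of either cycle (Section 5.2.3), and Section 6.4 expects GVHD in up to 60-70% of patients after DLI, although many such cases will not lead to a hold and restart. A hold that runs past the end of Cycle 1 could also fall under both rules, with two different starting doses.

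**Working it through.** The plan states no figure to reproduce here, so the check is arithmetic on its dosing tables.

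**Inputs.** Target 500 ng/kg/day (Section 5.2). Restart fraction 25-50% (Tables 7 and 8). Ramp 30, 60, 100, 200, 300, 400, 500 on Days 1-7 (Table 3). Steps every 4-6 hours (Table 6).

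1. **Restart dose.** 0.25 × 500 = 125 and 0.50 × 500 = 250 ng/kg/day. Against the ramp start: 125/30 = 4.2 and 250/30 = 8.3. Against the replaced lead-in start of 100: 1.25 and 2.5.

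2. **Shortest time from restart to 500**, assuming that the CRS protocol means Table 6 and every step is tolerated:
   - Grade 3 row, near doubling: 250→500 is 1 step, 4-6 h; 125→250→500 is 2 steps, 8-12 h.
   - Grade 1 row: 2 steps, 8-12 h.
   - Grade 2 row, following its worked example: 250→375→450→500 (or 125→312.5→425→500) is 3 steps, 12-18 h.
   - Overall 4-18 h. Table 3 takes 6 × 24 = 144 h from Day 1 to Day 7.

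3. **The two rules by time off drug:**

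| Time off | Mid-cycle GVHD hold | Between cycles |
|---|---|---|
| 72 h or less | 125-250, then step up | 500 at once |
| More than 72 h | 125-250, then step up | 30, ramp over 7 days |

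4. **Restart relative to the dose stopped, during a ramp.** Because the fraction is of target, a hold early in a ramp can restart above the dose that was stopped.

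| Ramp day (dose) | 125-250 ÷ stopped dose |
|---|---|
| 1 (30) | 4.2-8.3 |
| 2 (60) | 2.1-4.2 |
| 3 (100) | 1.25-2.5 |
| 4 (200) | 0.6-1.25 |
| 5 (300) | 0.4-0.8 |

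On unreduced Table 3 doses, this arises on Days 1-4 only. It mainly concerns Grade III acute GVHD, because the Grade II and moderate routes need at least 24 + 48 = 72 h before a hold.

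5. **Dose cost of a re-ramp.**
   - Shortfall against 500: 470 + 440 + 400 + 300 + 200 + 100 = 1,910 ng/kg.
   - Shortfall already incurred by a fast restart: from 250 × 4/24 = 42 (start 250, one 4 h step) to (375 + 187.5 + 75) × 6/24 = 159 (start 125, three 6 h steps).
   - Planned Cycle 1 dose: 1,090 + 22 × 500 = 12,090 ng/kg.
   - Net loss: (1,910 − 159)/12,090 = 14.5% to (1,910 − 42)/12,090 = 15.5%.
   - For a restart on Day 15, 14 × 500 = 7,000 ng/kg remains, and 1,910/7,000 = 27% of it is lost before netting.
   - A restart on Day 22 reaches 500 on Day 22 + 6 = Day 28.

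**The case against.** The strongest reply is that Tables 7 and 8 are a deliberate, specific rule: a 50-75% cut in previously exposed patients, then a step up. Section 1.1.7 calls both the 4-days-on/3-days-off and continuous schedules feasible, and says that after the Week 1 lead-in all cohorts stepped up to target on their assigned schedule. As described, patients resumed at target after weekly breaks with no re-ramp mentioned. That stands for breaks of up to 72 hours, where the GVHD rule is indeed cautious. It says nothing about longer gaps.

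Protections exist. Restart is permissive, premedication should be repeated after more than 24 hours off (Table 4 Day 1 includes dexamethasone 10-20 mg), Table 3 lets dosing be altered as clinically indicated, and Table 6 steps are taken as tolerated, with slower increases allowed. These reduce the risk, but none sets a re-ramp. There is also a real trade-off: Section 1.1.1 gives a median survival of 2-4 months without therapy, and slower dosing may cost responses.

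Three stronger readings are tempting, and the documents do not support them.

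- A reader might take the Table 6 instruction, "Discontinue the infusion if not resolved to Grade 1 within 72 hours", as showing that its steps were never meant to follow a longer gap. It is a stopping rule for unresolved Grade 3 CRS, not a limit on time off drug.
- A reader might argue from the short half-life in Section 8.1.3 that a long hold is close to a first exposure. No value is given, and the argument would not single out 72 hours.
- A reader might take 4-18 hours as the expected time to target. It is the minimum.

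**Conclusion.** The concern holds as a gap between two restart rules. Calling it a contradiction would go too far, because the 72-hour rule is written for the interval between cycles. For mid-cycle GVHD holds of more than 72 hours, Tables 7 and 8 allow a start 4.2-8.3 times the dose that the protocol requires after the same time off between cycles, and a return to 500 in as little as 4-18 hours against 144.

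This rests on two assumptions: that some holds exceed 72 hours and resolve with enough of the cycle left to restart, and, for the timing only, that the CRS protocol means Table 6 with steps tolerated without delay.

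Whether CRS would actually be more frequent or severe is unknown. The documents give no hold lengths and no CRS data after GVHD holds. Reactions typically came in the first 48 hours of the first infusion (Section 1.2.1), and steroids given for GVHD may blunt CRS. The restart above the stopped dose is a lesser and rare point. Overall this is a cheap improvement of modest severity.

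**What to change.** Add to Tables 7 and 8:

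*If flotetuzumab has been held for more than 72 hours, restart with the Table 3 ramp from 30 ng/kg/day (a faster restart only with PI approval and a documented reason). In all cases do not restart above the dose running when the infusion was held.*

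The first sentence extends the protocol's own between-cycle rule to mid-cycle GVHD holds; Table 6 needs no change. The cost is a short amendment, plus lost dose in patients held for more than 72 hours: about 15% of the planned Cycle 1 dose. A restart on Day 22 reaches 500 only on Day 28, and a later one does not reach it in that cycle, which could lower the chance of CR/CRi at the Cycle 1 Day 28 assessment. The protocol already accepts such a re-ramp between cycles, and the PI exception leaves room where the trade-off favours speed. The cap costs essentially nothing: on the unreduced schedule it matters only for a hold on Days 1-4 of a ramp, in Cycle 1 or a repeated Cycle 2 ramp.
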